6.3 Primary Estimand(s) - PrEP Comparison Component

6.3.1 First Primary Estimand

Primary Objective 1: To characterize PrEP adherence among HIV-uninfected young women during pregnancy and for twenty-six weeks postpartum, when provided with enhanced adherence support through mobile technology and counseling based on observed drug levels.	
Estimand description	The probability that pregnant and postpartum HIV-uninfected women will have optimal adherence to daily oral PrEP 1) at defined timepoints; 2) during pregnancy and postpartum (through twenty-six weeks) as measured in TFV-DP concentration levels in dried blood spots during periods when women are formally prescribed PrEP

Treatment	
 1. Daily oral PrEP (200 mg FTC/ 300 mg TDF) during pregnancy and/or postpartum. 2. Enhanced adherence support, including SMS messaging and feedback of drug levels with tailored counseling. 3. Behavioral HIV risk reduction package
Target population	Analysis set
Women who are pregnant and HIV-uninfected, 16-24 years of age, with a confirmed singleton pregnancy of 32 weeks' gestation or less and who have access to a mobile phone, are able to receive and read SMS messages, and express willingness to take PrEP anytime between pregnancy and 26 weeks postpartum	Adherence set: Women initiating PrEP
Variable(s)	Outcome measure(s)
TFV-DP drug concentration level	
 1. TFV-DP drug concentration level from Dried Blood Spots (DBS) measured in pregnancy at 4, 8, 12, 24, 36 week study visits, Labor and Delivery, and postpartum at 6, 14, and 26 week study visits during the periods that participants are receiving PrEP. A binary indicator, "optimal adherence" will be defined as TFV-DP levels meeting or exceeding the threshold of consistent dosing of PrEP ("Green Zone") determined in the PK Component (Appendix Tables 1-2). For women who are pregnant the threshold is 600 fmol/punch if on PrEP \leq 6 weeks and 650 fmol/punch if $>$ 6 weeks; for women who are not pregnant the threshold is 700 fmol/punch if on PrEP \leq 6 weeks and 1050 fmol/punch if on PrEP $>$ 6 weeks. 2. Visits with optimal adherence according to TFV-DP level during pregnancy and during postpartum
Handling of intercurrent events	Handling of missing data

 • Failure to start PrEP (in Cohort I or Cohort 2/Step 2) (Treatment policy strategy) • Discontinuation of PrEP: Only visits occurring prior to discontinuation of PrEP will be included. (While on treatment strategy) • HIV seroconversion: Only visits occurring up to the later of the date of first positive HIV test or date when PrEP is discontinued will be included. (While on treatment strategy) 	
Missing data could occur in the following situations:
 
 • Missing visit(s) when adherence would have been assessed • Missing drug concentration results due to sample collection or processing issues. 
Visits without adherence data will be excluded. Sensitivity analyses will be conducted imputing "suboptimal adherence" for each missed visit/concentration result

Population-level summary measure	Analysis approach

 1. Probability of optimal adherence according to TFV-DP levels in DBS at defined times during pregnancy and postpartum 2. Probability of optimal adherence while pregnant and up to 26 weeks postpartum 	
 1. At each visit that TFV-DP levels are obtained, the binomial proportion of women with optimal adherence will be calculated bounded by an exact (Clopper-Pearson) 95% confidence interval. 2. The binomial proportion of visits with optimal adherence in pregnancy and postpartum periods during periods when women are

	formally prescribed PrEP will be calculated with exact (Clopper-Pearson) 95% confidence intervals.
--	--

Supplemental Analyses:

- Exploratory longitudinal analyses identifying baseline and time-varying predictors of optimal adherence will be conducted with multivariable regression models which account for repeated measures across time for each participant.
- Adherence (as measured in TFV-DP levels) will also be summarized as a continuous outcome measure (median, IQR and mean [SD]) at each time point noted above when drug levels are measured, and “average” drug concentrations across pregnancy and postpartum periods, will be calculated, using generalized estimating equations as appropriate. Log transformation of this outcome will be considered if the distribution is not normal.
- Other approaches to summarizing the adherence outcome will be considered. This includes an ordinal variable with categories corresponding to different dosing levels (e.g., Below limit of quantification (BLQ), Red, Yellow, Green). For this type of outcome, at each visit that drug levels are measured in DBS, descriptive analyses will summarize the proportion of women in each adherence category (refer to categories in the appendix tables 1-2). For the interim analysis the proportion of women with TFV-DP levels below the limit of quantification (BLQ) at the week 12 visit will be estimated. Additional analyses with other cutpoints (e.g., below vs. above the limit of quantification; red vs. not red) will be considered.
- Women in Cohort 2 who later decide to initiate PrEP will be included in the main estimand. In addition, baseline characteristics, and patterns of adherence and duration on PrEP will be summarized separately for women in Cohort 1 and women in Cohort 2 who later decide to initiate PrEP using the approaches outlined above.
- The following additional descriptive statistics will be calculated: The proportion of women a) with at least one visit with TFV-DP levels corresponding to optimal adherence, b) who had TFV-DP levels corresponding to optimal adherence at all visits while formally prescribed PrEP, c) who had no detectable TFV-DP levels at any visit while formally prescribed PrEP d) who formally stopped PrEP among those who had initiated, including reasons for stopping, characterizing those who stop vs continue. In addition, mean follow-up time and % of follow-up time on PrEP will be summarized.

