### 1.3.3.1 PK Component Results

The PK Component evaluated PK characteristics of daily oral PrEP (FTC 200mg/TDF 300mg) among 20 pregnant (median gestational age: 18 weeks) and 20 postpartum (median time after delivery: 7 weeks) women at a median age of 20 years. Daily FTC/TDF was administered under direct observation for 12 weeks; of 3360 doses, 3352 [>99%] were directly observed). Weekly TFV-DP was measured from DBS using a validated liquid chromatography-tandem mass spectrometry assay. TFV-DP distributions were determined at 12 weeks and groups compared with the Wilcoxon test. Population PK models were fit to estimate half-life and steady state concentrations.

TFV-DP accumulated with a half-life of 15.3 days (95%CI: 12.8,17.8) in pregnancy and 18.0 days (95%CI: 15.3,20.7) postpartum, with steady state achieved by 8-10 weeks in both groups. Median TFV-DP was 965 fmol/punch (IQR: 691,1166) in pregnancy vs 1406 fmol/punch (IQR: 1053,1859) postpartum (p=0.006). Predicted median TFV-DP was 890 fmol/punch (IQR: 704,1143) in pregnancy vs 1418 fmol/punch (IQR: 1179,2139) postpartum. Under conditions of near perfect adherence, TFV-DP concentrations in DBS were approximately one-third lower in pregnancy compared to postpartum. TFV-DP levels in DBS observed in pregnancy also appeared lower than those reported in analogous studies of men and non-pregnant, non-lactating women in the US(167, 168).

These results confirm previous findings (see [Section 1.3.2](#)) that suggested drug levels in pregnant women may be lower than in a non-pregnant population. The PK Component results do not, however, provide information about PrEP efficacy among pregnant women, and data about the adherence-efficacy relationship during pregnancy remain limited.

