#### **9.1.4 Sample Size and Accrual-PK Component**

An important objective of the PK Component is to determine the TFV-DP concentration corresponding to optimal adherence. We will estimate the 25th percentile of the TFV-DP distribution in each of the two groups. [Table 2](#) shows estimated 95% CIs around the 25th percentile based on the normal distribution assumption at various sample sizes. With a sample size of 15 per group, the bounds of the 95% confidence interval are the 12th and 43rd percentile.

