If in the PK Component, TFV-DP variability at Week 12 appears high, this will be discussed among the CMC. For example, the team will decide if the threshold corresponding to adequate adherence should be set at the median or a different percentile instead of the 25th percentile.

In addition, antepartum and postpartum TFV-DP concentration thresholds corresponding to “excellent adherence” and the adherence categories for Weeks 4, 8 of the PrEP Comparison Component will be derived using the methods described above but from the distributions observed at Weeks 4 and 8 of the PK Component. For additional details on PK data analysis please refer to [Section 10.2](#).

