### **10.2 Study Design, Modeling and Data Analysis**

#### ***PK Component:***

All maternal participants will be administered once daily FTC/TDF. All doses will be DOT for the 12-week duration. DBS specimens will be collected at weekly intervals for analysis.

The goal is to quantify steady state TFV-DP in DBS.  $C_{ss}$  (drug concentration at steady state) will be determined by visual inspection of the plateauing of concentrations on the concentration time curve. Additionally, the following expression will be fit to the concentration time data,  $C_t = C_{ss} * (1 - e^{-K^* t})$ , where  $C_t$  is the drug concentration at time  $t$ ,  $C_{ss}$  is the fitted steady state drug concentration,  $K$  is the fitted first-order elimination rate constant. Half-life will be determined as  $\ln(2)/K$ . This model assumes first-order pharmacokinetics, which appears to be followed by TFV-DP in DBS (175). In addition, all available drug concentration samples will be utilized in a population pharmacokinetic model, thereby accounting for possible non-linearity and missed doses due to protocol deviations. Predicted  $C_{ss}$  from modeling will be subjected to the same analyses as above.

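### The SAP does not settle which adherence cut-off Labor and Delivery samples take, and neither candidate suits the days after birth; the source of the 600 cut-off used at Week 4 should also be stated.

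*SAP*

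**What the plan says.** SAP 6.3.1 defines the binary primary adherence outcome by four numbers, repeated in Appendix Tables 1-2. In pregnancy, "For women who are pregnant the threshold is 600 fmol/punch if on PrEP" for 6 weeks or less, and 650 beyond. For women who are not pregnant the pair is 700 and 1050, and Appendix Table 2 is headed for postpartum women. SAP 6.1 bases the steady-state cut-offs on the 25th percentile at 7 doses per week.

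The 6.3.1 visit list runs through the antepartum weeks, then Labor and Delivery, then the postpartum weeks. Pooled proportions are reported for pregnancy and postpartum. SAP section 4 accepts the Labor and Delivery visit from delivery through day 21. Protocol 6.2.1.4 allows 14 days, and Appendix X of the protocol extends this to 21.

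For the early cut-offs, protocol 9.1.6 says they "will be derived using the methods described above but from the distributions observed at Weeks 4 and 8 of the PK Component". If variability looks high, "the team will decide if the threshold corresponding to adequate adherence should be set at the median or a different percentile instead" of the 25th percentile. The Week 4 distribution itself is not printed. What is printed, in protocol 1.3.3.1, is "TFV-DP accumulated with a half-life of 15.3 days (95%CI: 12.8,17.8) in pregnancy and 18.0 days (95%CI: 15.3,20.7) postpartum"; "Median TFV-DP was 965 fmol/punch (IQR: 691,1166) in pregnancy vs 1406 fmol/punch (IQR: 1053,1859) postpartum"; and "Predicted median TFV-DP was 890 fmol/punch (IQR: 704,1143) in pregnancy vs 1418 fmol/punch (IQR: 1179,2139) postpartum".

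**The concern.** **Labor and Delivery.** The cut-off changes from 650 to 1050 at birth, but the drug level does not. With half-lives of 15.3 and 18.0 days, a sample taken soon after birth mainly reflects weeks of dosing in pregnancy. Applying 1050 would score many women who took every dose as suboptimal. Applying 650 late in the window would pass many who missed doses. The SAP does not clearly say which it does, or whether the visit counts in the pregnancy or the postpartum proportion.

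**Week 4.** This is the only antepartum visit targeted in the band of 6 weeks or less. If 600 lies above the lower quartile for fully observed dosing at day 28, some incomplete accumulation would be scored as missed doses.

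**Working it through.** **Inputs.** Half-lives and Week 12 quartiles from protocol 1.3.3.1; cut-offs from SAP 6.3.1; accumulation model from protocol 10.2, of which the protocol says "This model assumes first-order pharmacokinetics, which appears to be followed by TFV-DP in DBS".

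**The plan's own steady-state figures.** 1050 reproduces the observed postpartum lower quartile of 1053. The pregnancy value of 650 is lower than 691 observed (650/691 = 0.94) and 704 predicted (650/704 = 0.92), so it is somewhat lenient.

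**Labor and Delivery, more than 6 weeks on PrEP.** I assume that each quartile moves from its pregnancy value to its postpartum value with an 18-day half-life:

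C(t) = w × C_pregnancy + (1 − w) × C_postpartum, with w = 2^(−t/18).

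A log-normal is fitted at each day: σ = ln(Q3/Q1)/(2 × 0.6745), and the pass share is 1 − Φ(ln(cut-off/median)/σ). Women at 5/7 doses have levels multiplied by 5/7.

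Example, day 14, observed quartiles: w = 0.583. Median = 0.583 × 965 + 0.417 × 1406 = 1149. The quartiles are 842 and 1455, so σ = 0.405. For 650, ln(650/1149)/0.405 = −1.41, so 92.0% pass. For 1050, ln(1050/1149)/0.405 = −0.22, so 58.8% pass.

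Ranges below run over the predicted and observed quartile sets.

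| Day after birth | w | Full dosers passing 650 | Full dosers passing 1050 | 5/7 dosers passing 650 |
|---|---|---|---|---|
| 0 | 1.000 | 80.9-84.6% | 32.3-41.4% | 47.5-56.0% |
| 7 | 0.764 | 87.4-89.4% | 46.5-51.8% | 61.0-65.7% |
| 14 | 0.583 | 90.7-92.0% | 55.5-58.8% | 68.8-71.7% |
| 21 | 0.445 | 92.5-93.5% | 61.3-63.5% | 73.6-75.6% |

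A 25th-percentile rule should pass about 75% of full dosers. Throughout the window 1050 passes fewer and 650 passes more. Adding plain and split normal and split log-normal fits widens the full-doser ranges (day 0, 77-85% v 31-41%; day 14, 83-96% v 55-64%) without changing the picture.

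**Week 4.** Share of steady state at day t: f(t) = 1 − 2^(−t/half-life).

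- Pregnancy, 15.3 days: f(28) = 0.719 and f(84) = 0.978. Lower quartile at Week 4 = 691/0.978 × 0.719 = 508 (545 at 12.8 days, 477 at 17.8). From the predicted quartile: 704 × 0.719 = 506.
- At day 42, f = 0.851 and 691/0.978 × 0.851 = 601, so 600 fits the end of the band.
- Postpartum, 18.0 days: 1053/0.961 × 0.660 = 723 (774 at 15.3 days, 682 at 20.7), so 700 fits Week 4.
- At 15.3 days, 600 sits at about the 33rd to 43rd percentile of the modelled Week 4 distribution in pregnancy. The modelled median is 965/0.978 × 0.719 = 709, or 890 × 0.719 = 640 from the predicted median.

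**The case against.** **On delivery.** The cut-off rule turns on being pregnant or not, protocol 6.2.1.4 resets the calendar at delivery, and protocol 10.2 lists delivery apart from the visits made while pregnant. Read literally, 1050 applies, and the visit list can be parsed the same way. That has force, but it settles the label and not the fit: the literal reading puts a steady-state postpartum cut-off on samples taken in the first three weeks. The SAP still does not clearly assign the visit to a pooled proportion. The Analysis Implementation Plan may do so, but it is not among the documents. No printed data cover days 0-21, because the postpartum PK group enrolled 6-12 weeks after birth, so my pass rates are model results. Only women with a sample are affected: delivery bloods other than the HIV tests and plasma storage need not be repeated if a visit fell within the previous 30 days.

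**On Week 4.** A reader might infer that 600 is wrong, or that it departs from protocol 9.1.6. The documents do not support that. The rule rests on an observed distribution that is not printed, the team may choose another percentile, and independent panels reviewed the PK data before the component opened (protocol 9.3.3). The protocol sizes the lower quartile as a "percentile based on the normal distribution assumption at various sample sizes"; its Table 2 gives the 13th to 41st percentile for 20 women, which covers most of the 33rd-43rd. In a simulation of 20 women conditional on a Week 12 quartile near 691, the Week 4 quartile reached 600 in at most about 16% of sets at 15.3 days, up to about 38% at 12.8 and under 6% at 17.8. That is unlikely but not excluded. One could also read 600/650 as an accumulation ratio, which would need a half-life of 7.6 days, but no passage says the pair was built that way.

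A reader might also infer that the 75% hypothesis should be judged against the PK women's pass rate. With 20 women that is too imprecise: 12/20 has an exact interval of 36-81%.

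The SAP already reports each visit separately, with continuous levels and other categories, so a dip would be visible, though not its cause.

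**Conclusion.** The delivery point stands. The SAP leaves open which pooled proportion the visit enters, and either cut-off misclassifies women in a primary outcome. For full dosers the choice moves the modelled pass share from about 81-85% to 32-41% on day 0, and from 91-92% to 55-59% on day 14. Conversely, 650 passes about 70% of women at 5/7 doses by day 14. These sizes rest on quartiles from 20 women per group, log-normal levels, and washout towards postpartum levels that starts at birth with an 18-day half-life. The ambiguity itself needs no model. The effect on the pooled proportions depends on how many women have a delivery sample, which cannot be known in advance.

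The Week 4 point is a query. On the protocol's model 600 looks high for day 28 and right for day 42, while 700 fits day 28 postpartum. Only the unprinted Week 4 data can decide.

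**What to change.** For analysis only; counselling zones stay as they are.

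1. Reconcile the SAP 6.3.1 visit list with the pregnant/not-pregnant rule for Labor and Delivery samples, and state which period's pooled proportion the visit enters.
2. Pre-specify reporting that visit under both cut-offs by days since delivery, and show the pooled proportions with and without it.
3. Check 600 against the Week 4 PK data already held and state the percentile it represents.
4. Beside the Week 4 proportion, report the share of PK Component women, with an exact interval, who pass 600 at the same time on drug. This is descriptive context, so that incomplete accumulation is not read as missed doses, and not a replacement yardstick for the 75% hypothesis.
5. If 600 is not the Week 4 lower quartile, add a sensitivity analysis with the Week 4-derived value.

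The cost is a few sentences in the SAP and a small re-analysis of existing weekly PK data, with no new collection. In item 5 the analysis cut-off would differ from the counselling zone, and the report should say so.

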The primary objectives focus on women who initiate PrEP during pregnancy and continue through the first 26 weeks postpartum (Cohort 1). Adherence to PrEP will be assessed in this population by measuring TFV-DP drug levels in dried blood spots. Participants in this arm will receive an intervention designed to promote PrEP adherence, comprised of a) two-way SMS messaging related to PrEP adherence, and b) targeted adherence counseling guided by TFV-DP drug levels from past visits, refer to [Section 6](#). Participants will be contacted and provided with their DBS TFV-DP concentration results, as described in [Section 6.5](#). Less than adequate concentration results are defined during the PK Component by pharmacokinetic parameters established when drug adherence is measured using TFV-DP levels from dried blood spots.

Maternal participants who change their intent regarding PrEP will be allowed to do so. Participants in Cohort 1 who choose to stop PrEP will continue in follow-up undergoing the same procedures. If these participants later elect to resume PrEP, HIV-infection status must be confirmed before resuming PrEP, refer to [Sections 4.2.1](#) and [6.2.3](#). Maternal participants in Cohort 2 who subsequently choose to initiate PrEP will undergo a Step Change, during which eligibility for starting PrEP will be confirmed, refer to [Sections 4.2.3](#) and [6.2.3](#). These participants are referred to as Cohort 2/Step 2 and will follow the procedures for Cohort 1. These switches onto or off PrEP will be considered in the feasibility/acceptability outcomes, refer to [Section 9.2](#). While a formal step change will only be required when those originally declining PrEP later chose to initiate it, there is no upper limit set on the number of switches allowed. Switching will be closely monitored as part of feasibility and adherence outcomes.

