#### 6.2.3.1 Maternal Participants in Cohort 1 Who Subsequently Stop PrEP

To the extent possible, staff should try to identify the reasons for maternal participants choosing to stop PrEP. Once the maternal participant has stated that she is not willing to continue PrEP and the decision to stop PrEP will be entered into an eCRF. If not already required for the study visit at which this decision is made, the following additional study procedures should be conducted:

- iNSC
- TFV-DP level (DBS)
- HIV RNA test

This will not constitute a change from Cohort 1 to 2; the maternal participant will continue to be followed as per her original assignment per [Appendix IIA](#) with the exception of the following evaluations:

- iNSC with drug level feedback

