### Primary Objective 2.3.1:

- Women in Cohort 1 will comprise the analysis sample. A binary indicator, “optimal adherence” will be created, as defined above as TFV-DP levels in DBS meeting or exceeding the threshold determined in the PK Component as corresponding to protective levels of PrEP (24). At each visit that TFV-DP levels are obtained (see [Appendix IIA](#)), the proportion of women with optimal adherence will be calculated based on their TFV-DP levels at each visit. The proportion of visits with optimal adherence in the pregnancy vs. postpartum periods will be calculated and compared.
- Exploratory analyses identifying baseline and time-varying predictors of optimal adherence will be conducted with multivariable regression models using generalized estimating equations with a logistic link (to account for repeated measures across time for each participant).
- Adherence (as measured in TFV-DP levels) will also be summarized as a continuous outcome (median, IQR and mean [SD]) at each time point noted above when drug levels are measured, and “average” adherence across pregnancy and postpartum periods, will be calculated, using generalized estimating equations. We will focus on periods during which the participant has formally elected to be on PrEP. If a woman elects to formally stop PrEP (by notifying study personnel), periods of being formally off study drug will not be considered in adherence calculations.
- Other approaches to summarizing the adherence outcome will be considered. This includes an ordinal variable with categories corresponding to different dosing levels. For this type of outcome, at each visit that drug levels are measured in DBS, descriptive analyses will summarize the proportion of women in each adherence category, refer to categories discussed in [Section 9.1.6](#).

- Baseline characteristics, and patterns of adherence and duration on PrEP will be summarized separately for women in Cohort 2 who later decide to initiate PrEP using the approaches outlined above.
- The following additional descriptive statistics will be calculated: The proportion of women a) with at least one visit with TFV-DP levels corresponding to optimal adherence, b) who had TFV-DP levels corresponding to optimal adherence at all visits, c) who had no detectable TFV-DP levels at any visit.

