Regardless of cohort, all maternal participants will follow similar schedules of evaluations through the course of pregnancy and in the 26 weeks following delivery. Women in Cohort 2 may choose to initiate PrEP at any stage following study entry, and triggers for change in PrEP perceptions and acceptability over time will be recorded to better understand women's motivation to seek additional HIV prevention services. As Cohort 2 is not exposed to antiretroviral agents during pregnancy or postpartum, its unexposed time period will serve as a comparison group for estimates of incidence and prevalence of maternal and infant safety outcomes including a) pregnancy outcomes, b) maternal adverse events, and c) infant growth and development between the two exposure groups.

The primary objectives focus on women who initiate PrEP during pregnancy and continue through the first 26 weeks postpartum (Cohort 1). Adherence to PrEP will be assessed by measuring TFV-DP drug levels in dried blood spots. Participants in this arm will receive an intervention designed to provide participant-centered support, including support for PrEP use/adherence, comprised of a) two-way SMS messaging related to PrEP adherence, and b) targeted adherence counseling guided by TFV-DP drug levels.

Maternal participants who change their intent regarding PrEP will be allowed to do so. Participants in Cohort 1 who choose to stop PrEP will continue in follow-up. Maternal participants

in Cohort 2 who subsequently choose to initiate PrEP will undergo a Step Change, and will be referred to as Cohort 2/Step 2 and will follow the procedures for Cohort 1/Cohort 2 Step 2. While a formal step change will only be required when those originally declining PrEP later chose to initiate it, there is no upper limit set on the number of switches allowed for each participant. Switching will be closely monitored as part of feasibility and adherence outcomes.

There will be no randomization for this study. To monitor the balance of the maternal participants enrolled among various groups, the enrollment will be stratified by:

- Cohort: PrEP vs. No PrEP at enrollment
- Trimester of enrollment during pregnancy: 1st or 2nd trimester vs. 3rd trimester
- Country
- Age at enrollment: 16-17 years vs. 18 years of age and older

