- **Adherence Set:** All maternal participants on PrEP, including those in Cohort 1 and those in Cohort 2 who later decide to formally initiate PrEP. All visits/periods where maternal participants are actively prescribed PrEP.
- **Maternal Safety Set:** All maternal participants in Cohort 1 or Cohort 2, starting at enrollment
- **Infant Safety Set:** All liveborn infants in Cohort 1 or Cohort 2, starting at birth

5 General Considerations – PrEP Comparison Component

The primary analyses to address the primary objectives of the PK Component and the PrEP Comparison Component are outlined below. For a more detailed description of the analyses to be conducted, please refer to the Analysis Implementation Plan (AIP).

Categorical variables will be summarized as N (%), with corresponding 95% confidence intervals where applicable. Continuous variables will be summarized with means and standard deviations, medians and IQR (Q1, Q3), as well as min, max.

Descriptive summaries:

PK Component: We will summarize and compare demographic and clinical characteristics at enrollment between maternal PK Component Group 1 (enrolled in pregnancy) and maternal PK

Component Group 2 (enrolled postpartum). We will use Fisher's exact test to estimate differences in proportions and t tests or Wilcoxon rank-sum tests (as appropriate) for continuous measures.

PrEP Comparison Component: Entry demographic, pregnancy, pregnancy history, psychosocial, sexual behavior and partner characteristics of women in Cohort 1 and Cohort 2 will be summarized and compared using chi square tests (or Fishers exact test as appropriate) for discrete variables and t-tests or Wilcoxon tests for continuous variables.

6 Estimands and Estimation

6.1 Primary Estimand PK Component:

Primary Objective 1: To determine the concentration of tenofovir diphosphate (TFV-DP) associated with adequate adherence to FTC/TDF among women observed ingesting daily oral PrEP during pregnancy and postpartum.	
Estimand description	Maternal Steady state TFV-DP concentrations at Week 12
Treatment	1. Daily oral PrEP (200 mg FTC/ 300 mg TDF) during pregnancy and/or postpartum administered through direct observation.
Target population	Analysis set

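### Read literally, the discontinuation rule in SAP 6.3.1 excludes visits after a PrEP restart that the Adherence Set and the estimand itself include

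*SAP*

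**What the plan says.** **The rule.** In SAP 6.3.1, the intercurrent-event cell for stopping PrEP reads "Only visits occurring prior to discontinuation of PrEP will be included" and is labelled a while-on-treatment strategy. It does not say first or permanent discontinuation, and it does not mention restarts.

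**The other statements of scope.**
- SAP section 4, Analysis Sets, defines the Adherence Set to include "All visits/periods where maternal participants are actively prescribed PrEP".
- The estimand description in SAP 6.3.1 measures adherence "during periods when women are formally prescribed PrEP". The analysis-approach cell of the same table repeats this restriction.
- Protocol 9.2.6, under Primary Objective 2.3.1, says that "periods of being formally off study drug will not be considered in adherence calculations". It removes nothing else.

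**Restarts.** Protocol 3.2 provides for them in Cohort 1: "If these participants later elect to resume PrEP, HIV-infection status must be confirmed before resuming PrEP". It adds that "there is no upper limit set on the number of switches allowed", and SAP 2.1.2 says the same. After a Cohort 1 stop, protocol 6.2.3.1 states that "the maternal participant will continue to be followed as per her original assignment". The only scheduled item dropped is counselling with drug-level feedback, so TFV-DP sampling goes on. SAP section 7 lists PrEP restart as a report item.

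**Cut-offs.** Optimal adherence depends on time on PrEP. In pregnancy the cut-off is 600 fmol/punch up to 6 weeks and 650 after that. Postpartum it is 700 and then 1050. The SAP does not say how weeks on PrEP are counted after an interruption.

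**The concern.** A visit made on re-prescribed PrEP belongs in the analysis under four statements and is excluded by one. The one that excludes it sits in the estimand table, where a programmer would look for the rule. Two competent analysts could build different denominators for both primary summaries, the proportion of women at each visit and the proportion of visits in each period. The supplemental summaries in SAP 6.3.1 count visits while PrEP is formally prescribed, so a restarter's later visits could count there but not in the primary estimate.

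The direction matters. If women who stop and restart adhere less well than continuous users, leaving out their later visits raises the estimate, and the study hypothesis is that at least 75% reach a high level of adherence. Including those visits then raises a second question that the SAP leaves open: which cut-off applies while TFV-DP is re-accumulating.

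**Working it through.** **1. Apply the statements to one visit.** Take a Cohort 1 woman who formally stops, resumes after HIV status is confirmed, and has a DBS at a later scheduled visit.

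| Source | Is this visit counted? |
|---|---|
| SAP section 4, Adherence Set | Yes |
| SAP 6.3.1, estimand description | Yes |
| SAP 6.3.1, analysis approach | Yes |
| Protocol 9.2.6 | Yes |
| SAP 6.3.1, discontinuation row, read literally | No |

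**2. Reproduce the plan's precision figure.** Protocol Table 8 gives 68-81% for 75% adherence with n = 200. The exact (Clopper-Pearson) interval for 150/200 is 68.4-80.8%, which agrees.

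**3. Size of the contradiction.** Let *f* be the share of restarters among women on PrEP at a late visit, *c* the optimal proportion in continuous users and *r* that in restarters. The literal rule estimates *c*. The Adherence Set estimates (1 − *f*)*c* + *fr*. The difference is *f*(*c* − *r*). None of these inputs is in the documents, so the following are assumed scenarios with 200 women on PrEP and *c* = 75%.

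| *f* | *r* | Literal rule (95% CI) | Adherence Set (95% CI) | Difference (points) |
|---|---|---|---|---|
| 10% | 50% | 135/180 = 75.0% (68.0-81.1) | 145/200 = 72.5% (65.8-78.6) | 2.5 |
| 20% | 50% | 120/160 = 75.0% (67.6-81.5) | 140/200 = 70.0% (63.1-76.3) | 5.0 |
| 20% | 25% | 120/160 = 75.0% (67.6-81.5) | 130/200 = 65.0% (58.0-71.6) | 10.0 |
| 30% | 25% | 105/140 = 75.0% (67.0-81.9) | 120/200 = 60.0% (52.9-66.8) | 15.0 |

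If *r* = *c* the difference is zero.

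**4. When the weeks-on-PrEP count matters.** Protocol 1.3.3.1 gives a postpartum half-life of 18.0 days and a median of 1406 fmol/punch. Protocol 10.2 gives first-order accumulation. For a fully adherent median woman, *t* days after restart following a gap of *g* days:

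C = 1406 × [1 − 0.5^(t/18) + 0.5^(t/18) × 0.5^(g/18)]

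- *t* = 28, full washout: 1406 × (1 − 0.340) = 928.
- *t* = 28, *g* = 42: 1406 × (0.660 + 0.340 × 0.198) = about 1023.
- *t* = 28, *g* = 28: about 1090. With *g* = 7: about 1293.
- At *t* = 28 she is below 1050 only if *g* exceeds about 35 days. From full washout she passes 1050 at about day 36.

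So 928 and 1023 are optimal at 700 and suboptimal at 1050. Nominal postpartum DBS visits (delivery, then Weeks 6, 14 and 26) are 6, 8 and 12 weeks apart. A restart at one scheduled visit gives 1127, 1243 or 1351 at the next, even from full washout.

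In pregnancy (median 965, half-life 15.3 days), full washout plus 28 days gives 965 × (1 − 0.281) = 694, above both cut-offs. With the modelled median of 890 it gives 640, which is 10 below the later cut-off.

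**5. Why the count should not reset at every restart.** Take a woman dosing at 60% with a steady state of 0.6 × 1406 = 844, using the dose proportionality assumed in protocol 9.1.6. After a 7-day stop she is at 844 × 0.764 = 644. After 28 more days at 60% she is at 844 × 0.660 + 644 × 0.340 = about 776. A reset would judge her against 700 and call her optimal. At 1050 she is suboptimal.

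**The case against.** The strongest reply is that this is one loosely worded cell. Its while-on-treatment label can be read as leaving out only off-PrEP time, and every surrounding statement points that way. Coding detail is also deferred to the Analysis Implementation Plan, which is not among the documents. This stands as a guide to what was probably meant. It does not remove the problem, because the SAP never says which reading governs and the sentence itself refers to visits before discontinuation.

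Three stronger readings are tempting, and the documents do not support them.

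- **That the rule drops everything after a *first* discontinuation.** The word does not appear in the SAP, and a consistent reading is available.
- **That women who interrupt disappear from the analysis.** Their visits before the stop are kept under either reading. SAP 6.3.1 also summarises who stops, why, and the share of follow-up spent on PrEP.
- **That adherent restarters will generally be misclassified.** For the median woman this needs a gap longer than about five weeks and a postpartum visit within about five weeks of restart, which the nominal postpartum spacing does not produce. An off-schedule restart or a visit at the edge of its window could. A woman with a lower steady state is exposed for longer: at 1200, inside the observed IQR of 1053 to 1859, she needs 54 days from washout, since 1 − 0.5^(54/18) = 0.875 and 0.875 × 1200 = 1050.

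**Conclusion.** The point holds as an internal contradiction in the primary adherence estimand: the row is wrong as written and should be aligned before analysis. The contradiction is established by the text alone.

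Its numerical effect is not established. The range of about 0 to 15 percentage points rests wholly on assumed restart rates and restarter adherence. The top of that range needs 30% restarters with only 25% optimally adherent, and the effect could be negligible if few women restart or if they adhere as well as the others.

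The missing count of weeks on PrEP is a secondary gap. It bears mainly on the postpartum cut-offs, under the conditions worked out above, and it depends on first-order accumulation at the PK Component's median values.

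**What to change.** Replace the discontinuation row in SAP 6.3.1 with:

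*Visits during intervals when PrEP is not formally prescribed are excluded; visits after a documented restart are included.*

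This brings the row into line with the Adherence Set, the estimand description, the analysis approach and protocol 9.2.6.

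Add a sentence stating how weeks on PrEP (up to 6 versus more than 6) is counted after a restart. The count should depend on the length of the gap and should not reset automatically after a short stop. The pharmacologist can set the gap length from the PK Component half-lives.

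The cost is two SAP sentences and the matching derivation, with no change to visits or procedures. One point needs checking first. Protocol 6.2.3.1 records the decision to stop on an eCRF, but the documents do not show where a Cohort 1 restart date is recorded. SAP section 7 plans to report restarts, so the data source should be confirmed before the rule is programmed.
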